Association of Postoperative Anaemia with Patient Outcome in the RELIEF Trial

ClinicalTrials.gov Identifier: NCT04978285

Statistical Analysis Plan

28 September, 2021

BACKGROUND

Both preoperative anaemia and red cell transfusion are independent risk factors in major surgery. Patient blood management (PBM) aims to reduce the need for blood transfusion in an effort to improve patient outcomes. Australian PBM guidelines for the surgical patient are available, but there is no specific PBM guidance on the treatment of *postoperative* anaemia.

The consequences of *postoperative* anaemia remain unclear. Postoperative anaemia is more likely if there is pre-existing anaemia, but also increased perioperative blood loss, frequent blood sampling, excess IV fluids (leading to haemodilution), sepsis, and inadequate nutritional intake after surgery. A nadir in Hb concentration is most often observed within the first 3–4 days after surgery. Postoperative anaemia is believed to have deleterious effects on patient outcomes, including prolonged hospital stay, increased postoperative complications, and perhaps poor survival, but there is very little data to support this belief.

We therefore propose a study to investigate the incidence, extent, and outcomes of patients with anaemia after major surgery, including an assessment of the amount of IV fluids administered in the immediate perioperative period.

STUDY AIMS AND HYPOTHESES

Primary aim - To investigate the relationship between postoperative anaemia and patient-centred outcomes after major abdominal surgery.

Secondary aim – To determine whether a more liberal perioperative IV fluid strategy increases the risk of postoperative anaemia (haemodilution) at Day 3.

Hypothesis: Adults with anaemia in the immediate postoperative period following major abdominal surgery have a poorer quality of recovery and higher risk of complications, leading to poor disability-free survival when compared with patients without postoperative anaemia.

STUDY DESIGN

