A cohort study comparing patients with and without postoperative anaemia, using prospective data collected in a large, pragmatic, multicentre, randomized trial, the RELIEF trial, in which patients were randomly assigned to either a restrictive (zero balance) or liberal IV fluid regimen, stratified by site and planned HDU/ICU admission.⁵ The intention-to-treat population of the RELIEF trial will be utilised, namely all participants who were enrolled, randomised and underwent induction of general anaesthesia for eligible surgery.

Inclusion and exclusion criteria are as for the RELIEF trial.⁵

GROUP AND ENDPOINT DEFINITIONS

ANAEMIA GROUP DEFINITION

Postoperative anaemia will be defined according to the World Health Organisation definition (males Hb <130 g/L, and female Hb <120 g/L), as measured on postoperative Day 3, using the “Lowest Haemoglobin concentration”. Patients with missing Day 3 haemoglobin data will have these values imputed rather than these patients being excluded (details below).

A secondary group definition will be studied defined as patients with severe anaemia (Hb <100 g/L) at day 3 postoperatively.

LIBERAL PERIOPERATIVE IV FLUID GROUP DEFINITION

Liberal and restrictive perioperative IV fluid groups are defined as the corresponding randomised arms of the RELIEF trial. In brief, Liberal protocol group received a bolus of Hartmann’s balanced salt crystalloid 10 ml/kg at the commencement of surgery followed by 8 ml/kg/h administered until the end of surgery, and then maintenance infusion continued at 1.5 ml/kg/h for at least 24 hours. Patients assigned to the Restrictive protocol group received approximately half of this IV fluid volume.⁵

ENDPOINT DEFINITIONS

Primary endpoint

Persistent disability or death by 90 days, where persistent disability was defined as a WHODAS 2.0 score of at least 24 points (on the 48-point scale) at both 30 days and 90 days post-operatively,³¹ reflecting a disability level of at least 25% and being the threshold point between “disabled” and

“not disabled” as per WHO guidelines.³³ Disability was assessed by the participant, but if unable then we used the proxy’s report.

Secondary endpoints

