Secondary endpoints include an *a priori* composite of 30-day mortality or major septic complications (sepsis, surgical site infection, anastomotic leak, and pneumonia), plus each individually, acute kidney injury, ICU and hospital stay, unplanned admission to ICU, hospital readmission and quality of recovery (QoR-15).³⁰ We used the following definitions:

1. Death: all-cause mortality at 90 days, then up to 12 months after surgery
2. A composite (pooled) and individual septic complications: sepsis, surgical site infection, anastomotic leak, and pneumonia. [Detailed clinical definitions are provided in the Protocol]
3. Sepsis: using Centers for Disease Control and Prevention (CDC) with National Healthcare Safety Network (NHSN) criteria³⁴
4. Surgical site infection: using CDC criteria³⁴
5. Pneumonia: The presence of new and/or progressive pulmonary infiltrates on chest radiograph plus two or more of the following:
 - i. Fever $\geq 38.5^{\circ}\text{C}$ or postoperative hypothermia $<36^{\circ}\text{C}$
 - ii. Leucocytosis $\geq 12,000 \text{ WBC}/\text{mm}^3$ or leucopenia $< 4,000 \text{ WBC}/\text{mm}^3$
 - iii. Purulent sputum and/or
 - iv. New onset or worsening cough or dyspnoea.
6. Anastomotic leak: A defect of the intestinal wall at the anastomotic site (including suture and staple lines of neorectal reservoirs) leading to a communication between the intra- an extra luminal compartments.
7. Acute kidney injury: according to The Kidney Disease: Improving Global Outcomes (KDIGO) group criteria, but not urine output – for Stage 2 or worse AKI defined as at least 2-fold increase in creatinine, or estimated GFR decrease $>50\%$ ³⁵.
We will also report renal replacement therapy up to 90 days after surgery
8. Unplanned admission to ICU within 30 days of surgery
9. Total ICU stay: additive, including initial ICU admission and readmission times up to Day 30
10. Hospital stay: additive, from the start (date, time) of surgery until actual hospital discharge , plus readmission(s) up to Day 30
11. Quality of recovery: QoR-15 score³⁰ on Days 3 and 30
12. Hospital re-admission at 3, 6 and 12 months

PROCESS DATA CALCULATIONS

Red cell transfusions will be reported as dichotomous data (yes/no, where yes is any red cell volume $\geq 1 \text{ ml}$) data, and calculated for the intraoperative period plus recovery room (combined), and postoperative Days 1, 2 and 3.

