IV fluids (total volume) will be tabulated according to reporting in the RELIEF trial, for intraoperative plus recovery room (combined), and Days 1, 2 and 3.

Daily weight and CRP (if done) on Day 3 will be reported as mean (SD).

STATISTICAL ANALYSES

All statistical analysis will be performed with the intention-to-treat population of the RELIEF trial.⁵

Descriptive statistics will be used to compare the baseline and pre-Day 3 characteristics of patients with and without post-operative anaemia on Day 3, hereafter titled 'anaemia groups'.

The binary primary outcome, persistent disability or death to 90 days, will be compared between anaemia groups using log-binomial regression to estimate risk ratios and 95% confidence intervals directly, adjusting for RELIEF randomised group, age, sex, ASA physical status, Charlson score, preoperative aspirin, haemoglobin (baseline), type of surgery, planned HDU/ICU (either), and duration of surgery. Should the log-binomial model fail to converge, modified Poisson regression with robust standard errors will be used. Methods for addressing missing Day 3 anaemia are provided below.

Other binary endpoints (#1-8, 12) will be analysed similarly. Duration of stay outcomes (#9,10) will be summarised using medians and interquartiles ranges, and compared across anaemia groups using parametric accelerated failure time models with adjustment for the same factors. QoR-15 scores (#11) will be summarised using medians and interquartiles ranges, and compared across anaemia groups using median regression with robust standard errors.

To assess the secondary aim, the risk of postoperative anaemia at Day 3 will be compared between RELIEF randomised arms using proportions and analysis using log binomial regression adjusted for planned ICU/HDU admission.

Baseline and pre-Day 3 characteristics of patients missing the Day 3 anaemia assessment will be compared with those who have the measurement present. If there is evidence of missing Day 3 anaemia being dependent on these characteristics then multiple imputation of Day 3 anaemia will be performed using chained equations, including baseline and post-baseline variables predictive of either Day 3 anaemia being missing or of Day 3 anaemia itself (defined by correlation ≥ 0.30 for either), including the relevant outcome variables in the imputation models.

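### The randomised comparison of Day 3 anaemia adjusts for planned ICU/HDU only; adding baseline Hb and sex through a marginal risk-ratio estimator would narrow its interval modestly

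*SAP*

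**What the plan says.** The SAP's secondary aim is to learn whether liberal fluid "increases the risk of postoperative anaemia (haemodilution) at Day 3". Its Statistical Analyses section compares the randomised arms by proportions and "analysis using log binomial regression adjusted for planned ICU/HDU admission". The Protocol had the same comparison unadjusted, so the SAP has already taken one step towards baseline adjustment.

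In the same section the primary-outcome model is specified as "adjusting for RELIEF randomised group, age, sex, ASA physical status, Charlson score, preoperative aspirin, haemoglobin (baseline), type of surgery" and further covariates. The SAP Background states the prognostic link: "Postoperative anaemia is more likely if there is pre-existing anaemia".

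For convergence the SAP says "Should the log-binomial model fail to converge, modified Poisson regression with robust standard errors will be used". That sentence, and the pointer to the missing-data methods, sit in the primary-outcome paragraph. Day 3 anaemia is not among the numbered endpoints to which that approach is extended.

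On missing data, the Anaemia Group Definition says "Patients with missing Day 3 haemoglobin data will have these values imputed rather than these patients being excluded". Statistical Analyses imputes only if missingness is shown to depend on patient characteristics, with a model "including baseline and post-baseline variables predictive of either Day 3 anaemia being missing or of Day 3 anaemia itself", membership being set by a correlation of at least 0.30. The Protocol's Study Procedures list Hb preoperatively and on Day 1, with other laboratory tests left to clinical indication. No Day 3 Hb is listed as scheduled.

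**The concern.** This is the one main comparison in the plan that randomisation protects. The outcome is Hb dichotomised at a sex-specific cut-off, so baseline Hb is an obvious predictor of it. The plan names that predictor, records it and uses it elsewhere, but omits it here without giving a reason. The cost would be an interval somewhat wider than the recorded data allow, for an aim with no stated power or precision target. The comparison also inherits whatever is done about Day 3 values that were never measured.

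**Working it through.** **Inputs from the documents.** 3,000 patients allocated 1:1, so 1,500 per arm; anaemia below 130 g/L in men and 120 g/L in women; the covariate sets above. The 3,000 and its 80% power belong to the parent trial. No event rates, effect size or alpha are given, so that figure cannot be recomputed, and none exists for this aim.

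**Assumed inputs.** Day 3 anaemia 50–90%; correlation r between baseline and Day 3 Hb 0.3–0.65; Day 3 SD 15 g/L within sex; baseline SD 16 g/L; 30% planned ICU/HDU; two-sided 0.05.

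**1. Interval under the plan.** With equal risks p, SE(log RR) = √[2(1−p)/(1,500p)]. At p = 0.70 this is √(0.6/1,050) = 0.0239, and exp(±1.96 × 0.0239) gives 0.954–1.048.

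**2. Effect of adding baseline Hb and sex.** Simulated variance of log RR relative to the planned model, at r = 0.3 / 0.5 / 0.65:

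| Day 3 anaemia | Modified Poisson, complete data | Standardised logistic, complete data | Modified Poisson, 21% missing and imputed |
|---|---|---|---|
| 50% | .945 / .857 / .782 | .943 / .839 / .723 | .957 / .888 / .820 |
| 70% | .950 / .871 / .800 | .947 / .850 / .737 | .963 / .901 / .843 |
| 80% | .958 / .889 / .825 | .955 / .867 / .758 | .970 / .919 / .866 |
| 90% | .970 / .920 / .872 | .967 / .896 / .802 | .979 / .943 / .906 |

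Narrowing = 1 − √ratio:
- Modified Poisson: 1 − √.970 = 1.5% to 1 − √.782 = 11.6%.
- Standardised logistic: 1 − √.967 = 1.7% to 1 − √.723 = 15.0%.
- Modified Poisson after imputation: 1 − √.979 = 1.1% to 1 − √.820 = 9.4%.

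For modified Poisson with complete data, the equivalent in extra patients is 3,000 × (1/ratio − 1), or 93 to 836. Widening r to 0.2–0.8 widens the narrowing to about 0.6–25% across the two estimators.

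Modified Poisson intervals around RR 1.00:
- 70%, r = 0.5: 0.954–1.048 becomes 0.957–1.045.
- 50%, r = 0.65 (best): 0.931–1.074 becomes 0.939–1.065.
- 90%, r = 0.3 (worst): 0.976–1.024 becomes 0.977–1.024.

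Type I error was 0.040–0.061 for the planned model, 0.040–0.063 for modified Poisson and 0.039–0.061 for the standardised model.

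**3. Why the estimator matters.** The planned log-binomial model fitted in 240 of 240 simulated data sets. With baseline Hb and sex added it fitted in 4 of 240 (one standard solver). Forcing a bounded fit at 70% and r = 0.5 gave a mean RR of 1.044 against a crude 1.096. Using baseline anaemia as yes/no moved the RR from 1.158 to 1.150 (50%, r = 0.3) and from 1.095 to 1.069 (70%, r = 0.5). The risk ratio is not constant over baseline Hb, so this model no longer targets the marginal RR. Modified Poisson and standardisation stayed within about 0.005 of it.

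**4. Missing Day 3 Hb.** Take a true RR of 1.093 with p = 0.70 restrictive, hence 0.765 liberal.
- Hb measured in 85% of anaemic and 60% of non-anaemic patients in both arms: the complete-case risks are 0.6503/0.7913 = 0.8219 and 0.595/0.775 = 0.7677, RR 1.071.
- Measurement of the non-anaemic raised to 70% in the liberal arm only: RR 1.039. In the restrictive arm only: RR 1.112.

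**5. The 0.30 rule.** The correlation of baseline Hb with the binary outcome is r·φ(c)/√[p(1−p)], with c the normal quantile of p. It is .18–.24 at r = 0.3, .29–.40 at r = 0.5 and .38–.52 at r = 0.65, so on that route the rule admits baseline Hb in only part of the range. For arm, a 5-point risk difference at p = 0.70 gives about 0.05 × 0.5/0.458 = 0.05, so the rule alone would not admit it. Omitting arm pulls the imputed contrast towards the null.

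**The case against.** The plan's choice is defensible. Sex and baseline Hb are in the primary model because anaemia is not randomised; that does not make them necessary here. The mid-case change is in the third decimal of the limits. Every driver of the gain is assumed. Adjusting creates a convergence problem that the plan does not have, and the missing-data shifts in step 4 (0.02–0.05 in the RR) exceed the 0.003 change in the mid-case limits. Site, the other stratification factor, is also absent from this model.

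Most of this stands. The omission is not a defect, the gain is small at low correlation and high prevalence, and missing Day 3 Hb is the larger threat. Site is a separate small matter. What does not stand is that the point is mere preference: the variables are already collected, the SAP itself calls pre-existing anaemia prognostic, the gain held in every setting examined, and covariates chosen after seeing results would be less credible. The convergence problem is avoided by fixing a suitable estimator in advance.

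**Conclusion.** The point holds as a cheap, modest gain in precision. With complete data the interval narrows by about 1.5–12% (modified Poisson) or 1.7–15% (standardised logistic), and by about 1–9% (modified Poisson) with an assumed 21% missing and imputed. All of these rest on assumed prevalence and correlation.

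Four stronger readings are tempting and unsupported:
- That the planned comparison is biased for want of baseline Hb. Randomisation makes that adjustment unnecessary.
- That randomisation alone makes the comparison valid. No Day 3 Hb is listed as scheduled and the two SAP statements on imputation differ, so validity depends on the missing-data handling.
- That adjustment leaves the estimand alone whatever the model. That is true of the two estimators named, not of the log-binomial model.
- That a conclusion turns on it. The documents give no target effect or precision against which to judge that.

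A between-arm comparison of continuous Hb on Day 1 or Day 3 would be a different estimand and forms no part of this point.

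**What to change.** In the SAP's secondary-aim paragraph:
- Keep Day 3 anaemia as the outcome and prespecify adjustment for planned ICU/HDU, sex and baseline Hb.
- Name one estimator in advance: a logistic model standardised to a marginal risk ratio, or modified Poisson with robust standard errors. Do not add Hb to the log-binomial model.
- Keep the planned model, adjusted for planned ICU/HDU only, as a sensitivity analysis.
- State that the missing-data handling applies to this comparison, reconcile the two imputation statements, and include arm, sex and baseline Hb in the imputation model regardless of the 0.30 rule.

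The cost is SAP wording and a few extra models on recorded variables, with three downsides. The main estimator changes. Modified Poisson gave fitted risks above 1 for 0.2–19% of simulated patients, although its mean log RR stayed within 0.002 of the planned model's; the standardised logistic model avoids this. Patients without baseline Hb drop out unless it is imputed; the documents do not say how many there are, so the number should be reported.

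### The 0.30 correlation rule does not guarantee that the randomised arm enters the Day 3 anaemia imputation model, so imputed data can pull the secondary-aim comparison toward the null

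*SAP*

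**What the plan says.** The SAP, Statistical Analyses, makes imputation conditional: "If there is evidence of missing Day 3 anaemia being dependent on these characteristics then multiple imputation" of Day 3 anaemia by chained equations follows. Variables enter that model if they are "predictive of either Day 3 anaemia being missing or of Day 3 anaemia itself (defined by correlation ≥ 0.30 for either". One further group is named: "including the relevant outcome variables in the imputation models". Neither the randomised arm nor the remaining analysis-model covariates are named. The Protocol's Statistical Analysis section describes the same imputation without a threshold, and does not name the arm either.

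For the secondary aim, "the risk of postoperative anaemia at Day 3 will be compared between RELIEF randomised arms using proportions" and by log-binomial regression adjusted for planned ICU/HDU admission. The SAP does not say whether this uses imputed or observed data. Three statements bear on it:

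- Anaemia Group Definition: "Patients with missing Day 3 haemoglobin data will have these values imputed rather than these patients being excluded", with no condition attached and a pointer to later details.
- Statistical Analyses, opening: "All statistical analysis will be performed with the intention-to-treat population of the RELIEF trial".
- Statistical Analyses, primary-outcome paragraph only: "Methods for addressing missing Day 3 anaemia are provided below".

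On timing, the SAP has the liberal arm's "maintenance infusion continued at 1.5 ml/kg/h for at least 24 hours" after surgery. The Protocol, Study Procedures, has haemoglobin ordered before surgery and on Day 1, with further tests as clinically needed. It describes no routine Day 3 order.

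**The concern.** An imputation model should contain every variable of the analysis it serves. If the exposure is left out, imputed values are drawn as though exposure had no effect beyond what the other retained variables transmit. The estimated effect then moves toward zero.

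For the other endpoints, the outcome clause brings the outcome into the model. For the secondary aim that clause does not help, because the outcome is the imputed variable itself and the randomised arm is the exposure. The arm is an adjustment covariate of the primary model, but that places it in the analysis model, not the imputation model.

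This is the study's only randomised comparison. Attenuation here would favour concluding that liberal fluid does not raise the risk of anaemia.

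**Working it through.** **Inputs from the documents.** Allocation 1:1 (Protocol, Randomised group assignment); 3,000 patients (Protocol, Statistical Analysis), taken as 1,500 per arm; threshold 0.30 (SAP, Statistical Analyses). The plan gives no power or effect figure for this comparison, so there is none to reproduce; the 80% power quoted belongs to the parent trial.

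**Assumptions.** The documents do not give the prevalence of Day 3 anaemia, the arm effect, the missing fraction, or how much of the arm effect Day 1 haemoglobin carries. I assume 72.5% v 67.5% anaemia (risk difference, RD, 5.0 points; risk ratio 72.5/67.5 = 1.074) and vary the rest.

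**Step 1: can the arm pass the rule?** For a 1:1 arm and a binary variable with overall proportion p, correlation = RD / (2√(p(1−p))). Reaching 0.30 therefore needs RD = 0.6√(p(1−p)).

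| Overall anaemia | RD needed | Correlation at RD 5 | Correlation at RD 10 |
|---|---|---|---|
| 50% | 30.0 points | 0.050 | 0.100 |
| 70% | 27.5 | 0.055 | 0.109 |
| 85% | 21.4 | 0.070 | 0.140 |
| 90% | 18.0 | 0.083 | 0.167 |

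The same formula applied to missingness needs arm differences of 18.0, 24.0 and 27.5 points at 10%, 20% and 30% missing.

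**Step 2: nothing retained is related to the arm effect, and data are missing completely at random.** Imputed patients show no arm difference, so RD becomes RD × (1 − m) for missing fraction m. That gives 4.5, 4.0, 3.5 and 3.0 points at 10%, 20%, 30% and 40% missing. Risk ratios are 1.066, 1.059, 1.051 and 1.044. At 20%, for example: (0.8 × 72.5 + 0.2 × 70)/(0.8 × 67.5 + 0.2 × 70) = 72/68 = 1.059. This is not a worst case.

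**Step 3: Day 1 haemoglobin retained, arm not, missingness rising with Day 1 haemoglobin.** Large-sample simulation used assumed latent Day 1 to Day 3 correlations of 0.60 and 0.75. Day 1 haemoglobin then correlates −0.42 to −0.57 with anaemia, so it passes the rule in absolute value. Share of the full-data RD kept, across all runs:

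| Day 1 Hb carries | 20% missing | 30% | 40% |
|---|---|---|---|
| none of the effect | 76–77% | 64–67% | 53–56% |
| half | 87–89% | 82–84% | 76–79% |
| all | about 100% | about 100% | about 100% |

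With the arm added, about 97–103% is kept throughout.

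**Step 4: trial size.** n = 3,000, 30% missing, latent correlation 0.75, 600 replicates, 10 imputations, Monte Carlo error about 0.03 points. RD in points:

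| Day 1 Hb carries | Full data | Observed only | Rule | Arm added | Full minus rule |
|---|---|---|---|---|---|
| none | 5.04 | 4.76 | 3.35 | 5.14 | 1.69 |
| half | 5.04 | 4.48 | 4.22 | 5.11 | 0.82 |
| all | 4.99 | 4.36 | 5.09 | 5.13 | −0.10 |

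Hand check of the first row: 0.70 × 4.76 = 3.33, against 3.35. The loss slightly exceeds the missing fraction because the observed-data RD is itself below 5.04.

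The full-data standard error is √[(0.725 × 0.275 + 0.675 × 0.325)/1,500] = 1.67 points. The shortfall is therefore about 1.0 standard error (none carried) or 0.5 (half).

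The 95% interval excludes zero in 86–88% of simulated trials with full data. Under the rule it does so in 42% (none), 66% (half) and 85% (all). With the arm added, the figure is 76–77%.

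**Step 5: a different generating model.** Here missingness depends on baseline variables and Day 1 haemoglobin is absent, so this checks only the nothing-carried case. With the arm omitted, RD was 4.6, 4.0 and 3.4 points at 10%, 20% and 30% missing, against about 5.3 to 5.4 with full data or with the arm included. A fluid-volume proxy (assumed correlation about 0.7 with arm) correlated only about 0.04 with anaemia, so it would also fail the 0.30 rule.

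**The case against.** The strongest reply is that the harm needs several conditions together, and the documents settle few of them. Imputation must be triggered. The secondary aim must use it, yet the pointer to missing-data methods appears only under the primary outcome. The rule must be applied as exhaustive, although the text lists what to include and forbids nothing. The true effect must be non-zero. Day 1 haemoglobin must fail to carry the whole effect, although the fluid difference falls during surgery and at least the following 24 hours, so that measurement plausibly carries some of it. And the missing fraction must be material.

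All of this stands as a limit on size. With a null effect the gap cannot create a false positive. The 1.7-point and 42% figures belong to the least favourable of the three Day 1 haemoglobin scenarios. The good performance with the arm added is shown only under the simulated missingness mechanisms.

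It is also fair that analysing observed data alone would avoid this particular attenuation. In the Step 4 runs that kept about 87–94% of the RD (4.36/4.99 to 4.76/5.04). It would, however, sit badly with the SAP's statements that patients with missing values are not excluded and that all analyses use the intention-to-treat population.

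The reply does not remove the point. The SAP states a selection rule, and that rule, followed as written, would almost certainly omit the arm.

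**Conclusion.** The point holds in conditional form and should be fixed before analysis. If imputation is performed, used for the secondary aim and built literally by the rule, a true arm effect is attenuated by anything from about nil to the missing fraction or slightly more. For the assumed 5-point effect with 30% missing, that is about 0.8 points if Day 1 haemoglobin carries half and about 1.7 if none. Confidence is medium, because the effect size, missing fraction and share carried are all assumed.

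Three stronger readings are not supported:

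- That the SAP excludes the arm from imputation. It does not; it fails to guarantee entry, and an analyst may add it.
- That the secondary result will be biased. There is no such bias if the true effect is null, if the arm is added, or if imputed data are not used.
- That the primary risk ratio is biased. Adjustment covariates below 0.30 are likewise not guaranteed entry, but neither size nor direction of any bias can be fixed from the documents, and none is shown here.

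**What to change.** In the SAP, Statistical Analyses:

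1. State that each imputation model always contains every variable of the analysis it serves: randomised arm and planned ICU/HDU admission for the secondary aim; all adjustment covariates and the outcome for the other models.
2. State that an absolute correlation of at least 0.30 selects additional auxiliary variables only, such as Day 1 haemoglobin.
3. State that the secondary aim uses the imputed data whenever imputation is performed.
4. Reconcile this section, which imputes anaemia status conditionally, with Anaemia Group Definition, which imputes haemoglobin values without a condition.

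The cost is a few sentences and a slightly larger imputation model, with no new data. The downside is some precision if Day 1 haemoglobin does carry the whole arm effect: at 30% missing, 76% rather than 85% of simulated trials exclude zero.
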